10.1.2 Expectedness

Adverse events can be 'Expected' or 'Unexpected.'

Expected adverse events are those that have been previously identified as resulting from administration of the GVAX/placebo vaccine. For the purposes of this study, an adverse event is considered expected when it is a known risk associated with the GVAX/placebo vaccination, or is included in the informed consent document as a potential risk.

Refer to Section 6.1 for a listing of expected adverse events associated with GVAX/placebo vaccination.

For the purposes of this study, an adverse event is considered unexpected when it varies in nature, intensity or frequency from side effects that are expected after the GVAX/placebo vaccination. Refer to section 6.1 for a listing of expected adverse events associated with GVAX/placebo vaccination.

Adverse events occurring during vaccination or within 1 month of the last GVAX/placebo vaccination will be reported to the DFCI IRB according to DF/HCC policy.

10.1.3 Attribution

Attribution is the relationship between an adverse event or serious adverse event and the study treatment. Attribution will be assigned as follows:

- Definite The AE is clearly related to the study treatment.
- Probable The AE is likely related to the study treatment.
- Possible The AE may be related to the study treatment.
- Unlikely The AE is doubtfully related to the study treatment.
- Unrelated The AE is clearly NOT related to the study treatment.

10.2 Procedures for AE and SAE Recording and Reporting

Participating investigators will record and assess the occurrence of AEs at all participant evaluation time points during the study. Refer to section 9.0 for the evaluation time points.

As with all transplant patients, regardless of being on study, all grade ≥ 3 non-hematologic AEs and grade ≥ 4 hematologic AEs will be recorded in the participant's medical record and DFCI BMT data repository.

In addition, during and at 1 month after the last vaccination, adverse effects commonly associated with vaccination, as specified on the Vaccine Specific Toxicity Form (See Appendix I), will be recorded regularly regardless of grade.

The descriptions and grading scales found in the revised NCI Common Terminology Criteria for Adverse Events (CTCAE) version 5.0 will be utilized for AE reporting. All appropriate treatment areas should have access to a copy of the CTCAE version 5.0.

A copy of the CTCAE version 5.0 can be downloaded from the CTEP website at:

https://ctep.cancer.gov/protocolDevelopment/electronic_applications/docs/CTCAE_v5_Quick_Reference_5x7.pdf

10.3.1 Reporting to the IND-Holder and the FDA

- Site Responsible Investigators (or their designee) will forward all reportable events to both the Overall PI and the IND-Holder (or IND-Holder's designee) within 2 business days of knowledge of the event.
- The Overall Principal Investigator (or his designee) will forward all events occurring at the lead site to the IND-Holder, [name], or the IND-Holder's designee, within 2 business days of knowledge of the event. Additionally, the Overall Principal Investigator will ensure that all reportable events that are received from participating sites, which have not already been forwarded to the IND-Holder are sent to [name] (or his designee) within 2 business days.
- [name], as IND sponsor, will be responsible for all communication with the FDA. He will report to the FDA any adverse event that is serious, unexpected and reasonably related (i.e., possible, probable, definite) to the GVAX/placebo vaccination according to the FDA requirements.

10.4 Reporting to the NIH Office of Science Policy (OSP)

The IND Sponsor, [name], will be responsible for all communication with OSP. [name] will report to OSP, regardless of the site of occurrence, any adverse event that is serious, unexpected and reasonably related (i.e., possible, probable, definite) to the GVAX/placebo vaccination according to the OBA requirements.

10.5 Reporting to the Institutional Biosafety Committee (IBC)

Any adverse event that is serious, unexpected and reasonably related (i.e., possible, probable, definite) to the GVAX/placebo vaccination GVAX/placebo vaccination according will be reported to the IBC according to each IBC's requirements.

10.6 Reporting to Hospital Risk Management

Participating investigators will report to their local Risk Management office any subject safety reports or sentinel events that require reporting according to institutional policy.

11.0 DATA AND SAFETY MONITORING

11.1 Data Reporting

11.1.1 Method

The Clinical Research Coordinator will work together with the QACT to collect, manage, and monitor data for this study.

11.1.2 Data Submission

Allogeneic transplantation data will be collected for all patients enrolled on this study. These will include the allogeneic transplant data entered into the BMT repository via EDC-Inform. In addition to the transplant-specific data, the following research specific forms are required for this study:

Form	Submission Timeline
Eligibility Checklist	Complete prior to registration with QACT
Vaccine Specific Toxicity Form	Within 45 days of the last vaccination
Off Treatment/Off Study Form	Within 14 days of being taken off treatment or study.

11.2 Safety Meetings

The DF/HCC Data and Safety Monitoring Board (DSMB) will review and monitor study progress, toxicity, safety and other data from this trial. The board is chaired by a medical oncologist from outside of DF/HCC and has external and internal representation. Information that raises any questions about participant safety or protocol performance will be addressed with the Principal Investigator, statistician and study team members. Should any major concerns arise, the DSMB will offer recommendations regarding whether or not to suspend the trial.

The DSMB will meet twice a year to review accrual, toxicity, response and reporting information. Information to be provided to the DSMB may include: participant accrual, treatment regimen information, adverse events and serious adverse events reported by category, summary of any deaths on study, audit results, and a summary provided by the study team. Other information (e.g. scans, laboratory values) will be provided upon request.

11.3 Monitoring

Involvement in this study as a participating investigator implies acceptance of potential audits or inspections, including source data verification, by representatives designated by the DF/HCC Overall Principal Investigator or DF/HCC. The purpose of these audits or inspections is to examine study-related activities and documents to determine whether these activities were conducted and data were recorded, analyzed, and accurately reported in accordance with the protocol, institutional policy, Good Clinical Practice (GCP), and any applicable regulatory requirements.

All data will be monitored for timeliness of submission, completeness, and adherence to protocol requirements. Monitoring will begin at the time of participant registration and will continue during protocol performance and completion.

12.0 STATISTICAL CONSIDERATIONS

12.1 Endpoints

12.1.1 **Primary Endpoint**: The primary endpoint of this study is progression-free survival (PFS) at 18 months post-randomization. Progression-free survival is defined as time from randomization to progression of disease or death whichever occurs first. Patients with relapse/progressive disease who re-enter remission after vaccination or upon withdrawal of immune suppression alone will not be considered as having disease progression. The primary analysis will be performed using the modified intention-to-treat (ITT) principle, i.e., all transplanted and eligible patients who receive at least one vaccination will be included in the analysis according to the treatment arm they are randomized to.

12.1.2 **Secondary Endpoints**

- 12.1.2.1 Safety and toxicity of vaccination, as measured by the development of:
 - Grade II-IV and III-IV acute GVHD
 - CTC grade \geq 3 non-hematologic toxicity, or

- Grade \geq 4 hematologic toxicity attributable to vaccination
- 12.1.2.2 Biologic responses to vaccination following allogeneic stem cell transplant, as assessed by laboratory and histologic analyses of blood before and after vaccination, and skin biopsy samples at vaccination sites (Section 8.0). Serum and circulating mononuclear cells will be frozen prior to beginning vaccination and at regular intervals thereafter. Bone marrow aspirates will also be cryopreserved, if sufficient material is available.

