1.1 Study Design

GVAX vaccines will be generated by adenoviral vector mediated GM-CSF gene transfer into myeloblasts harvested from study subjects prior to admission for hematopoietic stem cell transplant Patients with Myelodysplastic syndromes (MDS) with excess marrow blasts or Acute myeloid leukemia (AML) not in remission are eligible. Leukemia cells will be harvested for vaccination generation after enrollment. Patients will be randomized (1:1) to GVAX versus placebo arm prior to The assignment of treatment arm will be blinded to the patients, treating transplant admission. physicians, nurses, research staff, and data assessors. Between the leukemia cell harvest and admission for allogeneic HSCT, patients are allowed to receive additional therapy (e.g. HMA therapy, chemotherapy etc.) at the discretion of the treating physician. Between day+30 to +60* after HSCT, patients with adequate hematologic recovery and no GVHD requiring systemic therapy will receive GVAX or placebo vaccine (normal saline) injections weekly x 3 week, then starting on week 5, every 2 weeks for 6 weeks, to complete a set of six total vaccinations. Patients will remain on tacrolimus for GVHD prevention during the vaccination period. Tacrolimus taper may commence after completion of vaccination, at the discretion of the treating physician, with the goal to be off immune suppression by 6-9 months post transplant in the absence of GVHD.

* Day 60 or next business day, if day 60 occurs on a weekend or holiday

1.2 **Primary Objective:**

Progression-free survival (PFS) at 18 months after randomization

1.3 Secondary Objectives:

- a) To assess the safety of vaccination following allogeneic (ablative or reduced intensity) stem cell transplantation
- b) To assess incidence of grade 2-4 and grade 3-4 acute GVHD, and chronic GVHD after vaccination following allogeneic stem cell transplantation.
- c) To assess PFS after start of vaccination
- d) To assess relapse and non-relapse mortality after vaccination
- e) To assess overall survival after vaccination
- f) To assess biologic activity of GVAX as compared to placebo vaccination after HSCT (see Section 8.0)

CONFIDENTIAL

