4.2 Registration Process for DF/HCC and DF/PCC Institutions

The QACT registration staff is accessible on Monday through Friday, from 8:00 AM to 5:00 PM Eastern Standard Time. QACT does not randomize after hours. Subjects must be registered between 8 A.M. and 5 P.M. Monday – Friday.

The registration procedures are as follows:

- 1. Obtain written informed consent from the participant prior to the performance of any study related procedures or assessments.
- Complete the protocol-specific eligibility checklist using the eligibility assessment documented
 in the participant's medical/research record. To be eligible for registration to the study, the
 participant must meet each inclusion and exclusion criteria listed on the eligibility
 checklist.

Reminder: Confirm eligibility for ancillary studies at the same time as eligibility for the treatment study. Registration to both treatment and ancillary studies will not be completed if eligibility requirements are not met for all studies.

3. Fax the eligibility checklist(s) and all pages of the consent form(s) to the QACT at [contact].

- 4. The QACT Registrar will (a) validate eligibility, (b) register the participant on the study, and (c) randomize the participant.
- 5. The QACT Registrar will send an email confirmation of the registration to the person initiating the registration immediately following the registration. Randomization result/ study arm assignment will be emailed to Cell Manipulation Core Facility (CMCF). All other study personnel will remain blinded to the study arm assignment.

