5.0 TREATMENT PLAN

- 5.1 Treatment can be administered on an either inpatient or outpatient basis. Expected toxicities and potential risks for irradiated, adenovirus vector transfected GM-CSF secreting autologous leukemia cell vaccination (GVAX) are described in Section 6 (Expected Toxicities and Dosing Delays/Dose Modification). No investigational or commercial agents or therapies other than those described below may be administered at the start of conditioning through vaccination with the intent to treat the participant's malignancy. Pre-treatment criteria/Pre-transplant
 - 5.1.1 **Pre-transplant evaluation**: All subjects enrolled on this study will undergo standard pre-transplant evaluation before the transplant date as required by Foundation for the Accreditation of Cellular Therapy (FACT) regulations and according the institutional standard operating procedure.
 - 5.1.2 **Randomization**: After enrollment, patients will be randomized in a 1:1 fashion to one of 2 arms on the study: "GVAX" vs. "Placebo". Randomization will be stratified by center (DFCI, BIDMC, MGH), disease, age (≥50 vs. <50), and conditioning intensity (myeloablative Flu/Bu4 vs. reduced intensity conditioning Flu/Bu2). Leukemia cell harvest will be performed on all patients regardless of their randomization status.
 - 5.1.3 **Leukemia cell harvest**: Blood for infectious disease marker (IDM) testing will be drawn prior to, or on the day of leukemia cell harvest. Leukemia cells for vaccine generation will be harvested via bone marrow aspiration and/or peripheral blood draw. Please note that the DFCI Cell Manipulation Core Facility can only accept collections Monday-Wednesday. The procedure for vaccine generation is detailed below:
 - 5.1.3.1 Bone marrow collection: 40 cc of marrow aspirate will be taken to collect leukemic blasts for vaccine generation and laboratory immune studies. If the patient's most recent marrow biopsy was performed within 2 weeks of the collection, an additional aspirate and core biopsy for routine clinical staging might be performed as a part of the marrow harvest at the discretion of the treating physician, and based on standard clinical practice.

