5.2 Allogeneic Hematopoietic Stem Cell Transplantation

- 5.2.1 Flu/Bu2 RIC Transplant: The reduced intensity conditioning regimen will consist of fludarabine (120 mg/m² total) and low dose intravenous busulfan (6.4 mg/kg total). Fludarabine 30 mg/m²/d will be administered as a bolus intravenous infusion once a day for 4 days on days -5, -4, -3,-2 (based on actual body weight). Busulfan 0.8 mg/kg (based on actual body weight) will be administered intravenously twice daily (approximately 12 hours apart) on day-5,-4,-3,-2 for a total of 8 doses. Since it is dose twice daily, it is suggested that the busulfan be administered first, with the fludarabine dose sandwiched in between. Fludarabine and busulfan can be diluted per institutional practice. The rate of the fludarabine and busulfan infusions can be done according to institutional practice. In conjunction with chemotherapy, patients will receive pre-hydration and intravenous fluids and/or diuretics as needed, and antiemetics as per institutional guidelines. Day 0 is defined as the first day of infusion of donor PBSC (or bone marrow). In instances where the donor product arrival is delayed, the day 0 of transplant may be pushed back a day. Donor PBSC or marrow cells will be administered according to standard practice. For PBSC products, the stem cell dose will be a minimum of 2x10⁶, with a recommended target of 5x10⁶ CD34+ cells/kg. For marrow products, the recommended target is 2 x 10⁸ TNC/kg.Following stem cell infusion, RIC SCT patients will receive GM-CSF 500 mcg SC qd starting on day +1, until absolute neutrophil count is>1000 on 2 consecutive values over 2 or more days. GM-CSF may be held if patient has circulating blasts, develops severe bone pain, or at the discretion of the transplant MD based on clinical judgment. Levofloxacin 500mg PO QD (or 250mg PO QD if CrCl < 50) or another antibiotic is recommended as bacterial prophylaxis until ANC is >500 μL. Prophylactic antibiotics for Pneumocystis carinii and HSV/VZV will be administered as per standard institutional guideline for RIC SCT. CMV PCR surveillance and preemptive therapy for reactivation should follow standard institutional guideline.
- 5.2.2 Flu/Bu4 Myeloablative transplantation- The myeloablative conditioning regimen will consist of Fludarabine and high dose intravenous Busulfan approximately q6hrs for 4 days, as follows:

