5.3 GVAX/Placebo Vaccination

Vaccination with GVAX or placebo vaccine will commence after hematologic recovery has occurred and the patient is between day +30 to day +60* post transplant. Vaccine administration can occur on an either inpatient or outpatient basis. At any time between day+30 to day +60*, the patient may undergo a bone marrow aspirate/biopsy and GVAX/placebo vaccination may commence provided the following criteria are satisfied:

* Day 60 or next business day, if day 60 occurs on a weekend or holiday

5.3.1 Criteria for starting GVAX/Placebo administration:

- No grade II-IV acute GVHD
- No systemic corticosteroid therapy*
- No uncontrolled acute infection
- No CTC grade ≥ 3 non-hematologic toxicity
- Absolute neutrophil count $\geq 500/\text{ul}$ off growth factor

- Platelet count ≥ 10 K/ul without transfusion.
- Absolute eosinophil count ≤ 5000/ul

Participants who do not meet the above criteria to start vaccination by day +60 will be considered "off treatment", and followed for survival.

5.3.2 **GVAX/Placebo Administration:**

- 5.3.2.1 Vaccinations will be administered weekly x 3 weeks, then q2weeks x 6 weeks for a total of 6 vaccines. The weekly scheduling of vaccination can be +/- 2 days for scheduling flexibility. A physician, PA, NP, RN, or research RN can administer the injections in either an outpatient or inpatient clinical setting. Injections will be administered according to standard nursing procedure in the patient's arms and thighs on a rotating basis. Injections must be performed without the prior application of EMLA or other topical or local anesthetics, as such compounds both could obscure local reactions to the vaccination and could cause reactions that might be interpreted as vaccine reactions. Approximately half of the vaccine dose should be administered subcutaneously, and remaining half the vaccine dose intradermally. It is suggested that about half of the vaccine be given first intradermally, and the rest subcutaneously by changing that angle of the needle.
- 5.3.2.2 Information regarding the number and location of the injections, the date of vaccination, route of administration, total volume of vaccine administered and vaccine site injection reactions will be collected for each vaccination and recorded in the patient medical record.

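### PFS is timed from pre-transplant randomization but analysed only in vaccinated patients, with no all-randomized PFS analysis stated and a wait, dosing span and clock in 12.5 that conflict with the protocol's schedule

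*Combined protocol and SAP*

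**What the plan says.** **Clock and population.** Section 12.1.1 defines PFS from randomization, reads it at 18 months and restricts the primary, modified ITT analysis: "all transplanted and eligible patients who receive at least one vaccination will be included in the analysis", by assigned arm.

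**When randomization happens.** Section 4.2 has the registrar, in one step, "b) register the participant on the study, and (c) randomize the participant". Section 5.1.2 agrees: "After enrollment, patients will be randomized in a 1:1 fashion to one of 2 arms on the study". Harvest comes later (Section 1.1: "Leukemia cells will be harvested for vaccination generation after enrollment"), and further therapy is allowed between harvest and admission, with no time limit given.

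**When vaccination happens.** Under Section 5.2.1, fludarabine is given "once a day for 4 days on days -5, -4, -3,-2"; the myeloablative regimen also starts on day -5. Under Section 5.3, "Vaccination with GVAX or placebo vaccine will commence after hematologic recovery has occurred and the patient is between day +30 to day +60". Section 1.1 gives three weekly doses, "then starting on week 5, every 2 weeks for 6 weeks, to complete a set of six total vaccinations".

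**Design assumptions.** Section 12.3 expects 152 enrolled to yield 106 able to start. Section 12.5 assumes 30-45 days from randomization to first dose and about 40 more for six doses, with little difference between arms in that time. It places the same 18-month effect once after randomization and once after HCT. It states 69 events and about 80% power at one-sided 0.15.

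**Other PFS analyses.** Section 12.8 lists several, none stated to be in all randomized patients. Objective 1.3(c) is "To assess PFS after start of vaccination", but 12.8 lists that analysis only for the case of non-proportional hazards.

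**Non-starters.** Section 5.3.1 takes them off treatment and follows them for survival. Section 5.7 removes them from study. Section 6.1.1.9 removes patients not engrafted by day +45. Section 11.1.2 collects transplant data for everyone enrolled.

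**The concern.** The time origin and the analysis set do not belong together. Entry to the set depends on an event, first vaccination, that happens weeks after the clock starts. The result describes neither patients as randomized nor patients from first dose.

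The patients left out are unlikely to be prognostically neutral. In the pilot (Section 2.4.2), 9 of 24 never started: 4 for rapid progression, 3 for acute GVHD, 1 for sepsis and 1 for pneumonitis. With no companion analysis and no counts by arm, a reader could not check whether the planned 30% attrition is balanced.

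The timing in 12.5 matters because a delayed effect costs log-rank power, and the stated delay is shorter than the protocol's own schedule allows.

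**Working it through.** **1. The plan's own figures.** Inputs are curves (1) and (2) of Section 12.5, t in months.
- S_A(18) = 0.459 and S_B(18) = 0.262: ratio 1.76, difference 19.8 points.
- Expected events with 53 per arm, uniform accrual over 45.6 months (3.8 years) and 18 further months: 29.1 + 40.2 = 69.2 (stated: 69).
- Simulated log-rank power, one-sided 0.15, 8,000 trials: 0.81 (stated: about 80%).
- Enrolment: 106/0.70, rounded up, = 152; 152/40 = 3.8 years.

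All reproduce.

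**2. Patients with no stated PFS analysis.** 152 - 106 = 46, or 30%.

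**3. Wait to first dose.** Randomization precedes admission and conditioning starts on day -5. The minimum wait is 5 + 30 = 35 days at the early end of the vaccination window and 5 + 60 = 65 at the late end, before adding harvest and interval therapy. Section 12.5 has 30-45. That range matches the pilot's start window counted from transplant (Section 2.4.2), which may be its origin.

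**4. Dosing span.** Doses fall on days 0, 7, 14, 28, 42 and 56, a span of 56 days against about 40 stated. The allowed shift of 2 days does not close the gap.

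**5. Last dose, days from randomization.** As stated: 30 + 40 = 70 to 45 + 40 = 85. By the schedule, at the minimum: 35 + 56 = 91 to 65 + 56 = 121. The gap S_A - S_B is 3.6 to 4.5 points at days 70-85 and 4.9 to 6.8 points at days 91-121.

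**6. Clock label.** Reading the curves 30 to 90 days earlier or later (assumed offset) moves 18-month PFS only to 25.2-27.9% for placebo and 45.5-46.7% for GVAX.

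**7. Sensitivity of power to the lag (assumption).** Let Arm A follow S_B until lag L and the conditional S_A afterwards, so its 18-month PFS is S_B(L) x S_A(18)/S_A(L). Other settings are as in step 1, with 4,000 trials per lag (Monte Carlo standard error below 0.01). The 18-month gap is taken against 26.2%.

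| Lag (days) | What it corresponds to | GVAX 18-month PFS | Gap (points) | Power |
|---|---|---|---|---|
| 30 | stated wait, short end | 45.2% | 19.0 | 0.78 |
| 45 | stated wait, long end | 44.8% | 18.6 | 0.76 |
| 65 | schedule minimum, late first dose | 44.0% | 17.8 | 0.73 |
| 85 | stated last dose, long end | 43.0% | 16.8 | 0.69 |
| 121 | schedule minimum, late last dose | 41.2% | 15.0 | 0.61 |

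**8. Companion analysis of all 152 (assumption).** If curves (1) and (2) describe starters and non-starters have equal PFS in both arms, the 18-month difference is 53/76 x 19.8 = 13.8 points. Log-rank power with 76 per arm is about 0.73: 0.726 if non-starters follow S_B, 0.736 if their median is 3 months with no cure. Assuming non-starter 18-month PFS of 5-20% and a median of 1.5-3.5 months gives 0.71-0.75. A normal-approximation comparison of 18-month rates gives 0.79-0.82.

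**9. Could exclusion differ by arm?** Vaccine is made only for GVAX patients (5.1.4). The minimum for six aliquots, 6 x 10^6 cells, is judged on yield after transduction (7.1.3). An insufficient second harvest takes a participant off study (5.1.3.4). The manufacturing facility knows the arm (4.2). Harvest is done in both arms (5.1.2), but no equivalent yield rule is stated for placebo.

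**The case against.** **The population is a declared choice.** The plan calls it modified ITT, analyses by assigned arm, plans for 30% attrition and describes the comparison as nondefinitive. The clinical start criteria are the same in both arms, are applied by blinded staff and precede exposure. This stands, and it is why the primary analysis need not change. A reader might infer that the death-free stretch biases the arm comparison. The documents do not show that: the stretch is present in both arms, and the pilot produced vaccine for every subject. Nor do they establish that the comparison is safe, because the yield rule in step 9 has no stated placebo counterpart.

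**The curves already carry a soft delay.** The initial hazards are 0.45 x ln2/2.5 + 0.1 x ln2/4.5 = 0.140 per month in Arm A and 0.76 x ln2/3.5 = 0.151 in Arm B, a ratio of 0.93. This stands in part. By 2 months the hazards are 0.106 and 0.135, a ratio of 0.79, which is before the schedule-based last dose and close to the latest schedule-minimum first dose (65 days).

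**The approximate wait overlaps the schedule.** The ranges 30-45 and 35-65 share 35-45 days. But 35-65 is itself a minimum, 30 cannot be attained, and the dosing span has no such overlap.

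**Several points are small.** The clock label barely moves the rates. Objective 1.3(c) is stated without condition, and the branch of 12.8 that carries it is the one the design expects. Removal from study need not end follow-up, since Section 5.6 follows vaccinated patients after removal. These stand; they are points of wording.

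**Conclusion.** The concern holds as a mismatch of clock and population, a missing companion analysis, and incorrect timing inputs in 12.5. It is worth fixing but does not undermine the design.

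Firm, from the documents alone: about 46 of 152 randomized patients have no stated PFS analysis; analysed patients cannot die before first dose; the wait is at least 35-65 days against 30-45; dosing spans 56 days against about 40; one target carries two clocks. Pre-dose progression is not excluded, because 5.3.1 has no disease-status criterion, so the guarantee covers death only.

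Conditional on assumption: power of 0.78 down to 0.61 under a sharp lag, and about 0.73 by log-rank for the companion analysis. A reader might infer that the sample size is miscalculated or that the trial is shown to be underpowered. Neither follows. The stated events and power reproduce, the curves contain no explicit lag term, and when benefit would begin is unknown. Equally, the plan's statement that its projection incorporates the wait gives no assurance, because the wait used is too short.

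Whether the null curve describes vaccination starters or all transplanted patients is not settled by the text, and the figures are not shown. No conclusion here rests on it.

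**What to change.** 1. Keep modified ITT as primary. Prespecify a companion PFS analysis of all randomized patients, from randomization and by assigned arm, described as diluted and likely below 80% power. Report non-starters by arm and reason, with harvest or manufacturing failure as a separate reason.
2. In 12.5, derive the wait and dosing span from the schedule in 5.2 and 5.3, use one clock for the 18-month target, state whether the null curve is restricted to vaccination starters, and restate power or give a range under the corrected lag.
3. In 12.8, list PFS from first vaccination (objective 1.3(c)) without condition.
4. Reconcile 5.3.1, 5.7 and 6.1.1.9 on the status of non-starters. Confirm that their relapse and death dates are captured, mostly through the transplant data of 11.1.2, and name a source for patients never transplanted.

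Cost: protocol wording and a little extra analysis. Sample size, primary analysis and visits are unchanged. The price is a less favourable stated power and a companion estimate that supports the primary result without replacing it.
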